8.2 Exclusion criteria

- 1) Any study ulcer of the NPUAP Stage I, II or IV
- 2) Diabetic ulcer or Venous ulcer (or stasis ulcer)
- 3) Past history of surgical treatment within 1 year or irradiation at the target pressure ulcer within 1 year
- 4) Hypersensitivity reaction to this product or povidone-iodine
- 5) Hyperthyroidism or thyroid disorder requiring drug treatment
- 6) Signs of a current underlying systemic infection (sepsis/bacterial infection/tuberculosis) or cellulitis or osteomyelitis
- 7) Type 1 diabetes
- 8) Current malnutrition
- 9) Heavy smoker: Current smoking level of ≥ 1 pack (20 cigarettes)/day of tobacco
- 10) Drug or alcohol addiction
- 11) Requirement of immunosuppressants during the study or current chemotherapy or radiotherapy
- 12) Application of other investigational product/medical device within 1 month prior to the

investigational device application (1d)

13) Pregnant or breastfeeding women

14) Other renal, hepatic, neurological, immunological disorder that may interfere with the wound healing process, at the discretion of the investigator

9. Target number of subjects and the rationale

The target number of subject enrollment is 20 subjects, with 10 subjects per group.

This study has a purely explorative goal so that no formal sample size calculation will be conducted but it was planned to enroll 10 subjects per group as the minimum sample size to achieve study objectives from a scientific perspective.

- ✓ Medifoam group: 10 subjects
- ✓ Betafoam group: 10 subjects

Even if a subject is withdrawn from the study, the subject will not be replaced.

10. Study method

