10.2 Investigational device application methods

[Investigational devices]

Medifoam[®] (Mundipharma)

Betafoam[®] (Mundipharma)

[General investigational device application method]

An appropriate type of the investigational device should be selected for the study ulcer size and it should be able to completely cover the target pressure ulcer. At every dressing change, record the selected investigational device size in the source document.

[Investigational device application sequence]

- ① Carefully wash the target pressure ulcer with normal saline.
- ② After washing, wipe the study ulcer for drying with sterilized gauze, if necessary. At this time, pay attention not to irritate the study ulcer.
- ③ Select a study device that is larger than the pressure ulcer, open the product packaging, take out the device using tweezers, and remove the release film. Directly cover the wound with the foam side without the release film, paying attention to completely cover the wound.
- ④ If necessary, fix around the edge of this product with surgical tape or Band-Aid while paying attention not to attach too tight to avoid skin irritation.
- ⑤ If there is a lot of exudate and a leak is likely to occur at the study ulcer, exchange the dressing more frequently than planned (twice weekly).

[Application frequency]

- Twice weekly

During the 12-week treatment period, dressing is performed twice weekly, but additional dressing changes are allowed, depending on the condition of the pressure ulcer, such as excessive exudates at the lesion. Nevertheless, the frequency of additional dressing is limited to twice per day. In case of additional dressing changes beyond twice weekly changes, the change frequency should be recorded in the Case Report Form.

On the weekly site visit days, the investigator (or clinical research coordinator) will change the dressing; on other occasions, the subject or guardian will perform self-dressing. The investigator (or clinical research coordinator) will train the subject or guardian on the dressing method at every visit.

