12.1 Schedule of study activities

12.1.1 Visit 1 (screening, -14d~0d)

Written Informed Consent Form should be first obtained from subjects prior to any test. Tests to be conducted at screening are as follows, and in case all tests are completed and test findings can be confirmed on the day of screening, Visit 1 and Visit 2 can be take place together. If Visit 1 and Visit 2 are taken place on the same day, duplicated tests (Physical Examination, Inclusion/Exclusion criteria, , Concomitant medication/treatment review) are only done once.

- ① Before involving a subject in the study, the subject will be informed of the study process and then the subject (or representative) will provide informed consent.
- ② Subject numbers will be assigned in the order of completing the Informed Consent Form.
- ③ Collect demographic information and medical history.
- ④ Conduct the physical examination.
- ⑤ As vital signs, measure blood pressure, pulse, and body temperature.
- ⑥ Conduct laboratory tests (hematology, blood chemistry). If test findings within 2 weeks prior to the consent date are available, they can be used instead.
- ⑦ Measure height and body weight of the subject.
- ⑧ Conduct a urine pregnancy test in women of child-bearing potential. Do not conduct the test in case the subject had menopause, hysterectomy, bilateral oophorectomy, or bilateral salpingectomy.
- ⑨ Take a photograph of the target pressure ulcer.
- ⑩ Check the NPUAP Stage and size (using a scale) based on the pressure ulcer assessment and confirm whether the subject meets the inclusion criteria.
- ⑪ Review concomitant medication/treatment.

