12.1.2 Visit 2 (enrollment, 1d)

Subject enrollment will take place at the second visit, and the following assessment will be conducted.

- ① Conduct the physical examination.
- ② Review the inclusion/exclusion criteria, and subjects who are finally determined eligible will go through the process of randomization.

- ③ Before applying the investigational device, check the infection signs using the CSSC(Clinical Signs and Symptoms Checklist).
- ④ Before applying the investigational device, take a photograph of the study ulcer, investigator will conduct a photo evaluation, and record the pressure ulcer size by a Scale.
- ⑤ After conducting standard dressing, apply the investigational device.
- ⑥ Record the baseline PUSH score.
- ⑦ Review concomitant medication and treatment-emergent adverse events.
- ⑧ Prescribe the investigational devices and train the subject or guardian on the self-dressing method.
- ⑨ Dispense the subject diary to record the frequency of position changes per day (if applicable) and the frequency of additional self-dressing.

12.1.3 Visit 3, 4, 5, 6, 7, 8, 9, 10, 11, 12, 13 (interim visit, 8d, 15d, 22d, 29d, 36d, 43d, 50d, 57d, 64d, 71d, 78d)

The following tests will be conducted at the interim visit. It can be replaced by home health care through coordinator's visit if the subject is not able to visit the institution.

- ① Conduct the physical examination.
- ② As vital signs, measure blood pressure, pulse, and body temperature.
- ③ Measure body weight (only 29d).
- ④ After removing the investigational device, take a photograph of the study ulcer, conduct the investigator's photo evaluation, and record the pressure ulcer size by a Scale and complete healing status.
- ⑤ Check the infection signs using the CSSC (Clinical Signs and Symptoms Checklist).
- ⑥ After conducting standard dressing, apply the investigational device.
- ⑦ After conducting the pressure ulcer assessment, record the PUSH score (15d, 29d, 43d, 57d, 71d).
- ⑧ Review concomitant medication and adverse events (all adverse events, local adverse events at the study ulcer).
- ⑨ Prescribe the investigational devices and train the subject or guardian on the self-dressing method.
- ⑩ At the last visit, investigational devices that have been prescribed but not used are to be returned.
- ⑪ Based on the subject diary, record the frequency of self-dressing beyond once-weekly in the Case Report Form.

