12.2.2 Laboratory tests, urine hCG test

Laboratory test and urine hCF test will be conducted once at screening and at study completion/early completion.

- Sample collection and documentation: Blood samples are collected from subjects according to the test schedule using an aseptic technique, and collected blood samples are analyzed in a QC-certified clinical pathology lab using commercialized hematology, blood chemistry test methods. Test findings are recorded in the Case Report Form and assessed for normal/abnormal status or clinical significance, and for clinically significant abnormal findings, the investigator's opinion will be recorded.
- Test parameters:
 - ① Hematology: WBC, RBC, WBC Differential count, hemoglobin, hematocrit, platelets
 - ② Blood chemistry: AST, ALT, ALP, creatinine, BUN, total bilirubin, glucose, protein, albumin, gamma GTP, TSH (TSH is conducted at screening only.)
 - ③ Urine hCG test (to be conducted in all women, except for those who have been menopausal for at least 1 year or had hysterectomy, bilateral oophorectomy, or bilateral salpingectomy)

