(13) Routine, long-term or broad use of this product is prohibited in pregnant women or women of childbearing potential or breastfeeding women.

(14) Concurrent use of this product with lithium, chlorhexidine, silver sulfadiazine compound, alkali, or mercury-containing agents may result in decreased antiseptic effects and discoloration. In addition, this product should not be used in combination with hydrogen peroxide.

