14.1 Discontinuation and withdrawal criteria

In case of meeting the following criteria for study device discontinuation, application of the study device and the study should be discontinued, and the reason for discontinuation and findings should be recorded in the Case Report Form.

- Criteria for discontinuation of the study device application

- 1) Acute reactions (allergy, hypersensitivity reactions, etc.) to the study device

- 2) It is determined that continuation of the study is difficult due to an accidental intercurrent condition.
- 3) It is determined that continuation of the study is impossible due to worsening of the pressure ulcer (Stage 4 or higher).
- 4) Debridement was performed during the study, after the study device application.
- 5) Pregnant during the study period
- 6) It is otherwise determined by the investigator that continued application of the study device is not appropriate due to reasons such as serious malnutrition, etc.
- 7) It is determined by the investigator that study participation is not appropriate due to a “serious adverse event”.

“Serious adverse event” is an event, irrespective of a causal relationship with the study device, that is as follows:

- ① Results in death or is life-threatening
- ② Requires inpatient hospitalization or prolongation of existing hospitalization
- ③ Results in persistent or significant disability or dysfunction
- ④ Results in congenital anomaly or birth defect
- ⑤ Other medically important events as identified by the Investigator

In case of discontinuation due to worsening of a pressure ulcer, the treating physician will ensure safety of the patient with appropriate tests and treatment, equivalent to the case of an adverse event.

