17.5 Pregnancies

In case a pregnancy occurring during study, the principal investigator should promptly report to Mundipharma Korea Ltd Product Safety Center within 24 hours of Investigator's knowledge of the pregnancy. If a subject becomes pregnant during clinical trial period, it is not considered Serious AE/AE but the subject should be discontinued. And the pregnancy, fetus and birth should be followed up and reported.

18. Indemnification Provisions

[APPENDIX 1] Subject Indemnification Provisions

19. Informed Consent Form and Subject Information Sheet

[APPENDIX 2] Informed Consent Form and Subject Information Sheet

20. Medical care and treatment criteria for subjects after the study

Subjects withdrawn from the study will be instructed to receive other appropriate treatment, and subjects who complete the study will be able to receive medical care as instructed by a treating physician, in case of a delayed, unexpected adverse event.

21. Measures for safety protection of subjects

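### The protocol prohibits routine or long-term Betafoam use in women of childbearing potential, yet its eligibility rules let them be randomised to 12 weeks of it

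*Protocol*

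**What the plan says.** The Betafoam precautions in Protocol 13.1, part C, item (13), read: "Routine, long-term or broad use of this product is prohibited in pregnant women or women of childbearing potential or breastfeeding women". Three groups are named.

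Exclusion criterion 13 in Protocol 8.2, with the same wording in the synopsis and in SAP section 4, reads: "Pregnant or breastfeeding women". Two groups are named.

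On exposure, Protocol 10.2 says: "During the 12-week treatment period, dressing is performed twice weekly". Extra changes are allowed if the ulcer needs them.

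On entry, Protocol 12.1.2 (Visit 2, step 2) says: "Review the inclusion/exclusion criteria, and subjects who are finally determined eligible will go through the process of randomization".

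Four provisions deal with pregnancy:

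- Protocol 12.1.1 (Visit 1): "Conduct a urine pregnancy test in women of child-bearing potential".
- Protocol 12.2.2 places the urine hCG test at screening and at study or early completion, for all women "except for those who have been menopausal for at least 1 year or had hysterectomy, bilateral oophorectomy, or bilateral salpingectomy".
- Protocol 14.1 lists as a reason to stop the device: "Pregnant during the study period".
- Protocol 17.5: "If a subject becomes pregnant during clinical trial period, it is not considered Serious AE/AE but the subject should be discontinued". The same section requires reporting within 24 hours and follow-up of the pregnancy and birth.

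**The concern.** The precaution restricts use according to childbearing potential, whereas the eligibility rule looks only at whether a woman is currently pregnant or breastfeeding. Applied correctly, the eligibility rule can therefore lead to treatment that another section of the same protocol prohibits on safety grounds.

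Other Betafoam restrictions in 13.1 do reappear as entry criteria: povidone-iodine hypersensitivity is exclusion 4, and thyroid disease is addressed in exclusion 5. The gap for women of childbearing potential is thus either an oversight or a decision that was not written down, and the reader cannot tell which. An investigator checking eligibility at Visit 2 has no rule on which text governs. What is at stake is participant safety and a clear eligibility rule, not the efficacy results.

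**Working it through.** The plan has no figure of its own to reproduce on this point, and Protocol section 9 states that no formal sample size calculation was made. The check compares the provisions and then counts the exposure.

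**Step 1. Which groups each text covers**

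| Group | 13.1 C(13), Betafoam | Exclusion 13 |
|---|---|---|
| Pregnant | Restricted | Excluded |
| Breastfeeding | Restricted | Excluded |
| Of childbearing potential, not pregnant or breastfeeding | Restricted | Not excluded |

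**Step 2. Can a woman in the third row enter?** Yes. Inclusion criterion 1 admits any adult from age 19, with no upper age limit and no menopausal condition. The screening hCG test is aimed at exactly this group, which makes sense only if they may enter. SAP Table 0201 tabulates possibility of pregnancy and contraceptive method by arm. With a negative test she passes Visit 2 step 2 and, under Protocol 10.3, can be allocated to Betafoam.

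**Step 3. Scheduled exposure if she neither heals nor withdraws early**

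- Site dressings on days 1, 8, …, 78: (78 − 1)/7 + 1 = 12.
- Self-dressings on days 5, 12, …, 82: (82 − 5)/7 + 1 = 12.
- Total: 12 + 12 = 24 applications, over 85 − 1 = 84 days.

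Protocol 10.2 allows additional changes on top of this, and 10.4 allows separate povidone-iodine where needed.

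**Step 4. Does any other provision close the gap?** The hCG tests, discontinuation on pregnancy and the reporting rule in 17.5 all respond to a pregnancy that already exists. None limits Betafoam exposure because of childbearing potential. The timing of the second hCG test is also unclear: 12.2.2 puts it at completion, the Visit 14 steps in 12.1.4 do not list it, and the column of the second mark in the schedule table cannot be recovered from the extracted text. No available passage requires contraception or explains why 12 weeks of scheduled use falls outside C(13).

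**Step 5. How likely is it that such a woman receives Betafoam?** The documents give no expected number, so let k be the number of women of childbearing potential among the 20 subjects (an assumption). With 10 subjects allocated at random to each arm, ignoring any blocking:

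P(at least one on Betafoam) = 1 − C(20 − k, 10) / C(20, 10)

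| k (assumed) | Calculation | Probability |
|---|---|---|
| 0 | none enrolled | 0% |
| 1 | 1 − 10/20 | 50% |
| 2 | 1 − (10 × 9)/(20 × 19) = 1 − 0.2368 | 76% |
| 3 | 1 − (10 × 9 × 8)/(20 × 19 × 18) = 1 − 0.1053 | 89% |

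**The case against.** The strongest reply is that C(13) is not an outright ban. It restricts three kinds of use, none of them defined, and it sits under warnings and precautions. The separate list of contraindications in 13.1 A does not mention childbearing potential. Treatment here is of one target ulcer of 3–100 cm², stops at healing, is seen weekly, and falls within the device's stated indication. A sponsor could argue that such use is neither routine, long-term nor broad. The lack of definitions stands as a fair point. But C(13) joins the three terms with *or*, so meeting one is enough, and a fixed twice-weekly schedule for up to 12 weeks is routine in the ordinary sense. If the sponsor reads it differently, the protocol should say so.

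Second, SAP Table 0201 lists contraceptive methods, and every row shown is a *yes* category. This suggests that contraception was expected of these women. A reporting table is still not an entry rule, and contraception alone would not meet a restriction based on childbearing potential.

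Third, the consent pages were not available and may hold a relevant condition. That limit stands: the finding covers the visible text only.

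Fourth, few or no such women may enrol. The protocol links pressure ulcers with aging societies (5.1) and expects subjects with physical impairment or dementia (21.13), so zero is plausible. This limits the practical impact but does not remove the conflict.

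Finally, Medifoam carries no such warning, so excluding these women from both arms may look excessive. But eligibility has to be settled before allocation, so a criterion that applied to one arm only would make the randomised groups differ by design.

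**Conclusion.** The concern holds. The protocol restricts Betafoam in women of childbearing potential, the eligibility criteria admit them, and nothing in the available text reconciles the two. An affected woman would have up to 24 scheduled applications over 84 days.

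This rests on reading a fixed twice-weekly schedule as routine use, and on the missing consent pages not containing a reconciling condition. The 50%, 76% and 89% figures illustrate the case where 1, 2 or 3 such women enrol; the actual number is unknown and may be zero. No endpoint, analysis or sample-size figure changes. The point should be fixed because it concerns participant safety and the remedy is cheap.

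**What to change.** Extend exclusion 13 to women of childbearing potential in the synopsis, Protocol 8.2 and SAP section 4. Use the definition already in 12.2.2, meaning all women "except for those who have been menopausal for at least 1 year or had hysterectomy, bilateral oophorectomy, or bilateral salpingectomy". Check the criterion at Visit 2 step 2, before allocation, and apply it to both arms.

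If the clinical and regulatory team concludes that C(13) does not bar 12 weeks of use on a single ulcer, write that justification into 13.1. In that case, add contraception and repeat hCG testing as entry conditions for both arms, and make the test timing agree across 12.1.4, 12.2.2 and the schedule table.

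The cost of the exclusion is one line in each place, matching consent wording, Institutional Review Board approval of the amendment, and possibly a small loss of eligible subjects.

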13.2 Medifoam®

A. Contraindications

In case of rash, pyrexia, allergic reactions or infection symptoms while using this product, use of this product is prohibited and appropriate treatment should be instituted as instructed by a physician.

B. Precautions and warnings

(1) As the status of exudate absorption can be observed from the back side of this product, exchange a dressing when the exudate has been absorbed or expanded to about 90% of the margin.

(2) In case of severe bleeding, use the product after hemostasis.

(3) On an infected wound (wound with symptoms such as flare, swelling, pain, feeling hot, strong malodor and pus discharge), use this product after eliminating the cause of bacterial proliferation such as a foreign substance, pus, or necrotized tissue.

(4) As this product is for single-use only, re-use is prohibited.

14. Discontinuation/withdrawal criteria and early completion criteria

14.1 Discontinuation and withdrawal criteria

In case of meeting the following criteria for study device discontinuation, application of the study device and the study should be discontinued, and the reason for discontinuation and findings should be recorded in the Case Report Form.

- Criteria for discontinuation of the study device application

- 1) Acute reactions (allergy, hypersensitivity reactions, etc.) to the study device

- 2) It is determined that continuation of the study is difficult due to an accidental intercurrent condition.
- 3) It is determined that continuation of the study is impossible due to worsening of the pressure ulcer (Stage 4 or higher).
- 4) Debridement was performed during the study, after the study device application.
- 5) Pregnant during the study period
- 6) It is otherwise determined by the investigator that continued application of the study device is not appropriate due to reasons such as serious malnutrition, etc.
- 7) It is determined by the investigator that study participation is not appropriate due to a “serious adverse event”.

“Serious adverse event” is an event, irrespective of a causal relationship with the study device, that is as follows:

- ① Results in death or is life-threatening
- ② Requires inpatient hospitalization or prolongation of existing hospitalization
- ③ Results in persistent or significant disability or dysfunction
- ④ Results in congenital anomaly or birth defect
- ⑤ Other medically important events as identified by the Investigator

In case of discontinuation due to worsening of a pressure ulcer, the treating physician will ensure safety of the patient with appropriate tests and treatment, equivalent to the case of an adverse event.

14.2 Early completion criteria

Subjects who achieve complete healing* of the target pressure ulcer will terminate the study early. Subjects who can terminate the study early will conduct all tests scheduled for the End-of-Study (85d) visit and then complete the study.

(* Complete healing: Defined as the condition with the epithelial tissue covering 100% of the study ulcer, no abrasion or ulceration, intact dermis and epidermis.)

15. Statistical analysis methods

15.1 General principles of result analysis

Data obtained from subjects in this study will be analyzed as the SS(Safety Set) and the FAS(Full Analysis set).

- 1) In the SS(Safety set), data obtained from subjects who were enrolled in the study, had at least

- 1 application of the study device, and had at least 1 safety assessment will be analyzed.
- 2) In the FAS(Full analysis set), data obtained from subjects who were enrolled in the study, had at least 1 application of the study device and then had at least 1 available endpoints of main interest review will be included in analysis.

Efficacy and demographics will be analyzed using the FAS and safety data will be analyzed using the SS.

For subjects with a missing value during the study or who are withdrawn from the study prior to study completion, efficacy analysis will be conducted by applying the LOCF (Last Observation Carried Forward), only in case such subjects have available endpoints of main interest assessment results after the investigational device application. However, in case of missing values for Other endpoints and safety endpoints, raw data will be used for analysis, without applying LOCF.

